#### **7.5.2.8 Proportion of Subjects Achieving a Facial IGA of Clear (0) or Almost Clear (1) With at Least a 2-Grade Decrease from Baseline at Each Visit**

The frequency and percentage of subjects achieving a facial IGA of clear (0) or almost clear (1) with at least a 2-grade decrease from baseline will be summarized at each visit. The difference in percentage between each dose of imidolimab and placebo will be estimated by an unadjusted risk difference in proportions with 90% exact unconditional CIs. This will be performed overall and within each facial IGA stratum (Grade 3 or 4). The common risk difference will also be tested using a generalized CMH test (ANOVA for row means), adjusting for facial IGA at baseline (Grade 3 vs. 4).

An additional exploratory analysis will be performed by visit for the proportion of subjects achieving a facial IGA of clear (0) or almost clear (1) with at least a 2-grade decrease from baseline. A repeated measures generalized estimating equations (GEE) model with a logit link will be used. The model will include treatment, visit, treatment by visit interaction, and baseline facial IGA score as categorical covariates. Data from protocol-specified visits up to Week 20 will be included in the analysis. An unstructured correlation matrix will be used to model correlation within a subject; if convergence is an issue, a Toeplitz structure may be considered. An odds ratio resulting from this model along with 90% CI will be reported.

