### 7.5 Efficacy Analyses

The ITT Analysis Set will be used as the primary analysis set for all efficacy analyses. Per protocol analyses will be performed on the primary as well as the following secondary endpoints:

- Change from Baseline in facial inflammatory lesion counts at visits other than Week 12
- Change from Baseline in facial noninflammatory lesion counts at each visit
- Change from Baseline in total facial lesion (inflammatory and noninflammatory lesions) counts at each visit
- Change from Baseline in facial IGA at each visit
- Proportion of subjects achieving a facial IGA of clear (0) or almost clear (1) with at least a 2-grade decrease from Baseline at each visit

No adjustment for multiplicity will be made.

All statistical tests will be performed at the 10% level of significance unless otherwise stated. All confidence intervals (CIs) will be reported as 2-sided 90% CIs unless otherwise stated. Descriptive statistics will be provided for the continuous variables as number of subjects, mean, SD, standard error of the mean, first and third quartiles, minimum, and maximum. Descriptive summaries of continuous variables will be shown for baseline, change from baseline to endpoint, and percent change from baseline to endpoint. All data will be listed in data listings.

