### **7.5.3 Exploratory Efficacy Analyses**

The continuous data endpoints of change and percent change from baseline will be analyzed using the MMRM approach as described for the primary efficacy analysis in [Section 7.5.1](#). Summary statistics and the results of statistical testing at each visit will be provided for each continuous exploratory variable. In addition, the change from baseline in PGI-S and Truncal PGA (by body region as well as the overall and the worst score across three regions) will be summarized and analyzed by shift tables and ordinal logistic regressions as described in [Section 7.5.2.7](#). Baseline of the response variable will be added to the ordinal logistic regression model as a categorical variable. The overall Truncal PGA will be presented separately for all subjects, adolescents, and adults.

The frequency and percentage of subjects for subjects for categorical exploratory endpoints related to Truncal PGA (by body region as well as the overall and the worst score across three regions), facial IGA, PGI-C, PGI-S, SSQ, and SSRS will be summarized at each protocol-specified visit. For proportion of subjects in each response category for the SSQ and SSRS, the difference in distribution between each dose of imidolimab and placebo will be analyzed using the approach described for the proportion of subjects in each response category for the PGI-C in [Section 7.5.2.9](#). For other categorical exploratory endpoints, an unadjusted risk difference and 90% exact unconditional CIs will be estimated between each dose of imidolimab and placebo for all subjects and within each stratum for facial IGA at baseline (Grade 3 vs. 4); the common risk difference will also be tested using a generalized CMH test as described in [Section 7.5.2.8](#).

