Logistic Regression with GEE using PROC GENMOD	<pre> PROC GENMOD DESCENDING;   CLASS SUBJECT TRT VISIT BASE;   MODEL Y= BASE TRT VISIT / LINK=LOGIT DIST=BIN;   REPEATED SUBJECT=SUBJECT / TYPE=UN;   LSMEANS TRT VISIT / DIFF CL ALPHA=0.1;   ODS OUTPUT LSMEANDIFFS = LSDIFS ESTIMATES=EST LSMEANS=LSMEANS PARAMETERESTIMATES=PE; RUN; Where TRT is treatment, VISIT is the study visit number, and BASE is the baseline of outcome variable. </pre>
Ordinal Logistic Regression using PROC LOGISTIC	<pre> PROC LOGISTIC;   CLASS TRT BASE BASEFIGA;   MODEL Y = TRT BASE BASEFIGA; RUN; Where Y is the ordinal outcome variable, TRT is treatment, BASEFIGA is the facial IGA score at baseline, BASE the baseline of outcome variable. Remove BASEFIGA from the model if outcome variable is facial IGA. </pre>

Test	Template SAS Code for Modeling (SAS Version 9.4)
Cochran-Mantel-Haenszel ANOVA statistics (row means score)	<pre>PROC FREQ;   TABLES BASEFIGA*TRT*X/CMH2 ALPHA=0.1; RUN; </pre> 
Where BASEFIGA is facial IGA at baseline, TRT is treatment, and X is the outcome variable.

Exact unconditional CI	<pre>PROC FREQ;   TABLES TRT*X/ RISKDIFF(CL=EXACT) ALPHA=0.1;   EXACT RISKDIFF; RUN; </pre> 
Where TRT is treatment, and X is the outcome variable.

Obtaining generalized risk difference	<pre>PROC FREQ;   TABLES TRT*X / ALL LIST MISSING ALPHA=0.1;   TEST SMDCR; RUN; </pre> 
Where TRT is treatment, and X is the outcome variable.

Weighted Kappa and confidence interval	<pre>PROC FREQ;   WEIGHT COUNT;   TABLES BASEFIGA*TRT*X/AGREE ALPHA=0.1; RUN; </pre> 
Where BASEFIGA is facial IGA at baseline, TRT is treatment, and X is the outcome variable.

Test of treatment difference for agreement	<pre>PROC FREQ;   TABLES BASEFIGA*TRT*X/CMH2; RUN; </pre> 
Where BASEFIGA is facial IGA at baseline, TRT is treatment, and X is the Cicchetti-Allison weight of outcome variable. Cicchetti-Allison weight = 1-abs(CHG)/(k-1), where k = number of categories of the outcome variable.

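### The main IGA responder difference is unadjusted while its test is stratified by baseline IGA; separately, the exact 90% interval as coded may sit well above its nominal level when response rates are low

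*SAP*

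**What the plan says.** **Estimate and interval.** SAP 7.5.2.8 plans an "unadjusted risk difference in proportions with 90% exact unconditional CIs" for each dose against placebo. The next sentence extends this to the strata: "This will be performed overall and within each facial IGA stratum (Grade 3 or 4". SAP 7.5.3 repeats the method for most other binary endpoints: "an unadjusted risk difference and 90% exact unconditional CIs will be estimated between each dose".

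**Test.** SAP 7.5.2.8 continues: "The common risk difference will also be tested using a generalized CMH test (ANOVA for row means), adjusting for facial IGA at baseline". SAP 7.5 sets the level: "All statistical tests will be performed at the 10% level of significance unless otherwise stated". Intervals are two-sided 90%.

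**Code.** In SAP Appendix 2 the interval template is "TABLES TRT*X/ RISKDIFF(CL=EXACT) ALPHA=0.1", with no stratum variable and no score option. The test template is "TABLES BASEFIGA*TRT*X/CMH2 ALPHA=0.1", with baseline IGA as the stratum.

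**Other IGA-aware analyses.** SAP 7.5.2.8 adds a GEE logistic model with baseline IGA as a covariate, giving an odds ratio with a 90% CI. SAP 7.1, item 1(d), measures the effect in the imputed datasets by Somers' d pooled over the IGA strata. For a binary outcome, that is a stratum-pooled risk difference.

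**Protocol.** Section 9.4.6.1 paired exact 90% intervals with an exact test. The SAP kept the interval and replaced the test, and SAP section 8 does not list the replacement.

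**The concern.** Two separate things look wrong.

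1. **The main estimate does not match its test.** Randomisation is stratified by baseline IGA. A Grade 3 subject needs a two-grade fall to respond and a Grade 4 subject needs at least three, so the stratum probably matters for this endpoint. The p-value respects the stratum; the headline difference and interval printed beside it do not.

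2. **The interval may not have its stated level.** An exact unconditional interval can be built on the raw difference or on a score statistic. The raw-difference version can be very conservative at low response rates, and the code does not say which is meant.

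A Phase 2 development decision leans on estimates and intervals. If an interval that includes 0 is printed beside a p-value below 0.10, and no rule says which governs, readers will have to choose for themselves.

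**Working it through.** **Inputs.** 120 subjects randomised 1:1:1 with 10% loss before Week 12 (SAP 3.5) gives 120 x 0.9 / 3 = 36 per arm. Alpha is 0.10 and intervals are 90% (SAP 7.5). The documents give neither IGA responder rates nor the Grade 4 share. Rates are therefore varied (placebo 5-50%, active 5-70%), and Grade 4 is taken as 20% for the conflict figures below.

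**The plan's own figure.** The only power statement concerns the primary endpoint. With a difference of 6.1, SD 10.4 and 36 per arm, 6.1 / (10.4 x sqrt(2/36)) = 2.49, and Phi(2.49 - 1.645) = 80%. The noncentral t gives 79.4%. This supports 36 per arm as the working size. It says nothing about the responder endpoint.

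**Why the raw-difference interval is wide.** Its lower limit exceeds 0 only if the maximum over a common rate of P(X1 - X2 >= d) is at most 5%, with both counts binomial on 36. That maximum is 6.2% at d = 7 and 3.8% at d = 8. So active must lead by 8 responders (8/36 = 22 points) whatever the placebo rate. The worst-case rate is used even when observed rates are far lower.

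**Coverage of the nominal 90% interval.** Full enumeration of the 37 x 37 tables, inverting two one-sided 5% tests on the raw difference:

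| Placebo v active | Coverage |
|---|---|
| 5% v 5% | 100.0% |
| 10% v 20% | 98.7% |
| 10% v 25% | 98.2% |
| 10% v 30% | 97.8% |
| 20% v 40% | 95.2% |
| 30% v 50% | 93.5% |
| 40% v 60% | 92.9% |

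The lowest value in the grid is 91.8%. With the score statistic, the exact interval covers 90.4-92.4%.

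**One dataset, treated as a single stratum: 10/36 v 4/36.** The pooled rate is 14/72 = 0.194 and the difference is 0.167. CMH = [0.167^2 / (0.194 x 0.806 x 2/36)] x 71/72 = 3.15, so p = 0.076. The raw-difference exact interval is -4 to 36 points (width 40). The Newcombe interval is 1 to 31 points (width 30, or 25% narrower). With placebo at 4/36, CMH reaches p<0.10 from 10/36, but the exact interval excludes 0 only from 12/36.

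**Conflict with the stratified CMH test.** 200,000 simulated trials per scenario, 36 per arm, 20% Grade 4:

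| Placebo v active (approx.) | p<0.10 but interval includes 0, all trials | As share of CMH-significant trials |
|---|---|---|
| 10% v 20% | 24.1% | 70% |
| 10% v 30% | 25.0% | 35% |
| 17% v 31% | 16.6% | 40% |
| 17% v 38% | 14.9% | 23% |
| 27% v 46% | 9.8% | 18% |
| 40% v 60% | 4.2% | 8% |

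The reverse conflict was 0.0% throughout.

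**Which feature causes it.** An unadjusted asymptotic interval set against the same stratified CMH test gives this conflict in at most 2.5% of trials. The score-based exact interval is also unadjusted, yet it cuts the conflict to 1.3-5.4%. The choice of exact statistic is therefore the main cause, and missing stratification explains little.

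**Check of the alternative.** A Mantel-Haenszel difference with Sato variance removes the conflict (0.0%), with the reverse conflict in 0.2-5.4% of trials. Its coverage is 88.2-89.4%.

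**The case against.** - **The strata are not ignored.** A reader might infer that the SAP never estimates a stratified difference. The documents do not support that: within-stratum intervals, an IGA-adjusted odds ratio and an IGA-pooled Somers' d are all planned. What stands is that the pooled risk difference is confined to a sensitivity analysis, while the main overall difference is unadjusted.
- **The interval follows the protocol.** Protocol 9.4.6.1 asks for exact intervals. The mismatch arose when the SAP changed the test. This is correct, and it is a reason to keep the exact interval as supportive and to record the change of test.
- **The statistic is not fixed.** The text of 7.5.2.8 is satisfied by a score-based exact interval, and Appendix 2 calls its code a template to be completed before signoff. This stands: the over-coverage is conditional on the unstandardised default.
- **The rates are unknown.** If both arms respond at 40-60%, coverage is about 93% and conflict is rare. This also stands, so only a range can be given.
- **The consequence is limited.** The endpoint is secondary and SAP 3.3 calls such testing exploratory. The interval errs on the cautious side only, so it does not create false positive claims.

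**Conclusion.** The point holds in two parts. First, on the text alone, the main overall difference and interval for the IGA responder endpoint are unadjusted while the accompanying test is stratified by IGA; 7.5.3 carries the same mismatch to other binary endpoints. Second, if the code runs on the unstandardised difference, the nominal 90% interval at 36 per arm covers roughly 92-100% over the assumed rates. It then disagrees with the CMH test in about a quarter of trials at 10% v 20-30% and about 4% at 40% v 60%.

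A reader might infer that leaving out the strata causes the over-coverage, or that 98% is a fixed property of the plan. Neither follows. The exact method causes the excess, and the figure depends on rates that the documents do not give and on a software default that is assumed here. The primary analysis is not affected.

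**What to change.** 1. In SAP 7.5.2.8, make the Mantel-Haenszel IGA-stratified risk difference with a 90% stratified Newcombe or stratified score interval the main estimate, printed beside the CMH p-value.
2. Keep the protocol's exact interval, overall and within strata, as supportive. Name the score statistic in both the text and Appendix 2.
3. Apply the same to the binary endpoints in 7.5.3 that use the unadjusted difference.
4. State which result governs if the interval and p-value disagree.
5. Record in SAP section 8 the change from the protocol's exact test to CMH.

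The cost is a stratified table request, a score option and edits to three SAP sections and the code appendix. No data collection changes. The downside is that coverage becomes approximate when the Grade 4 stratum is sparse. The Sato-variance version, at about 88-89%, shows the size of that, and it should be disclosed if that version is chosen.

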#### **7.5.2.9 Proportion of Subjects in Each Response Category for the PGI-S at Each Visit**

The frequency and percentage of subjects in each response category for the PGI-S will be summarized at each visit. The difference in distribution between each dose of imidolimab and placebo will be compared using a Wilcoxon rank-sum test and Somers' D statistic which may be interpreted as a generalized risk

difference. This will be performed over all subjects and within each stratum for facial IGA (Grade 3 or 4). The common risk difference will also be tested using a generalized CMH test (ANOVA for row means), adjusting for facial IGA at baseline (Grade 3 vs. 4).

#### **7.5.2.10 Proportion of Subjects in Each Response Category for the PGI-C at Each Post-Baseline visit**

Proportion of subjects in each response category for the PGI-C at each post-Baseline visit will be summarized and analyzed using the approach defined for the proportion of subjects in each response category for the PGI-C, as described in [Section 7.5.2.9](#).

#### **7.5.2.11 Change from Baseline in DLQI/CDLQI at each visit**

Change from baseline in DLQI/CDLQI total score at each visit will be analyzed separately as well as together using a similar MMRM model as specified for the primary endpoint in [Section 7.5.1](#).

### **7.5.3 Exploratory Efficacy Analyses**

The continuous data endpoints of change and percent change from baseline will be analyzed using the MMRM approach as described for the primary efficacy analysis in [Section 7.5.1](#). Summary statistics and the results of statistical testing at each visit will be provided for each continuous exploratory variable. In addition, the change from baseline in PGI-S and Truncal PGA (by body region as well as the overall and the worst score across three regions) will be summarized and analyzed by shift tables and ordinal logistic regressions as described in [Section 7.5.2.7](#). Baseline of the response variable will be added to the ordinal logistic regression model as a categorical variable. The overall Truncal PGA will be presented separately for all subjects, adolescents, and adults.

The frequency and percentage of subjects for subjects for categorical exploratory endpoints related to Truncal PGA (by body region as well as the overall and the worst score across three regions), facial IGA, PGI-C, PGI-S, SSQ, and SSRS will be summarized at each protocol-specified visit. For proportion of subjects in each response category for the SSQ and SSRS, the difference in distribution between each dose of imidolimab and placebo will be analyzed using the approach described for the proportion of subjects in each response category for the PGI-C in [Section 7.5.2.9](#). For other categorical exploratory endpoints, an unadjusted risk difference and 90% exact unconditional CIs will be estimated between each dose of imidolimab and placebo for all subjects and within each stratum for facial IGA at baseline (Grade 3 vs. 4); the common risk difference will also be tested using a generalized CMH test as described in [Section 7.5.2.8](#).

### **7.5.4 Sensitivity Analyses**

A number of sensitivity analyses are planned to evaluate the robustness of the primary and secondary efficacy results.

For the primary efficacy endpoint, the following sensitivity analyses will be performed:

- Analysis of primary efficacy endpoint using the PP Analysis Set.
- Analysis of primary efficacy endpoint for adolescent subjects (age <16 years).
- Analysis of primary efficacy endpoint by age group ([12, 25) years,  $\geq 25$  years).
- Analysis of primary efficacy endpoint by age and sex (male and [12, 25) years, male and  $\geq 25$  years, female and [12, 25) years, female and  $\geq 25$  years)
- Sex (male, female) will be added to the MMRM as a categorical variable if this model can converge.

- Site will be added to the MMRM as a fixed categorical effect if this model can converge. Small sites (enrollment less than 5 subjects) will be pooled together.
- Smoking history (current smoker vs non-current smoker) will be added to the MMRM as a fixed categorical effect if this model can converge.
- The papule and pustule count will be summed and analyzed using a similar MMRM model as specified for the primary analysis for ITT Analysis Set.
- Multiple imputation with FCS method ([Section 7.1](#)).
- Tipping point analysis ([Section 7.1](#)).
- Prior to database lock and unblinding, the assumption of normality in the change from baseline in facial inflammatory lesion count will be checked by visually inspecting the distribution of the residuals. If the normality assumption is not met, a repeated measures model using a GEE approach with an alternative distribution or any transformation will be considered. An unstructured correlation matrix will be used in the model if GEE is decided to be used; a Toeplitz structure may be considered if convergence is an issue. However, the results from the primary efficacy analysis will be considered the primary efficacy results.

For the secondary efficacy endpoints listed in [Section 7.5](#), the following sensitivity analyses will be performed:

- Analyses of secondary efficacy endpoints using the PP Analysis Set.
- Multiple imputation with FCS method ([Section 7.1](#)).

### 7.5.5 Subgroup Analyses

Subgroup analyses will be carried out but only for the primary efficacy endpoint. Each subgroup will be analyzed separately using descriptive statistics. No hypothesis tests will be performed. Subgroup variables that will be examined include:

- Baseline Facial Inflammatory Lesion Count:
  - ≥ Median value
  - < Median value
- Age groups:
  - [12, 18) years
  - [18, 30) years
  - ≥30 years
- Sex groups:
  - Male
  - Female
- Baseline facial IGA:
  - Grade 3
  - Grade 4
- Race:
  - White
  - Non-white
- Prior systemic oral antibiotics:
  - No
  - Yes

- Prior systemic oral retinoid:
  - No
  - Yes

## 7.6 Pharmacokinetic Analyses

The PK analysis will be performed for subjects in the PK Analysis Set.

Mean trough serum concentration-time data for samples collected on Days 29, 57, and 85 will be tabulated as well as graphically presented as scatter plots. Nominal collection times will be used for graphs.

A subject listing of all concentration-time data following SC injections will be presented by subject and scheduled sample collection time. All concentration data of imsidolimab will be summarized by day and nominal time point using the number of observations, arithmetic mean, SD, CV, minimum, median, maximum, geometric mean, and CV of geometric mean. Concentration time data values reported as below the limit of quantification (BLQ) that occur at pre-dose or prior to the first observed non-BLQ positive concentration will be set to zero or will be set to missing for records that occur after the last quantifiable concentration.

## 7.7 Immunogenicity Analyses

ADA status and titer values will be listed by subject and time point. ADA incidences (overall, treatment-emergent, and treatment-boosted) will be tabulated as absolute occurrence (n) and proportion (%) of subjects by treatment group and visit. Descriptive statistics including number of subjects, mean, median, SD, minimum, and maximum of the titer values by treatment group and visit, where possible, will be provided. Neutralizing antibodies, if assayed and present, will also be summarized. The relationship between changes in PK profile and treatment-emergent positive responses will be evaluated to identify a potential impact ADA on imsidolimab exposure. Box plots of ADA status relative to trough concentrations will be plotted. Where possible, evaluation of ADA impact on efficacy and safety may be performed and summarized separately.

All immunogenicity results will be listed.

## 7.8 Biomarker Analyses

Biomarker analyses will be performed by a third party designated by the Sponsor. A separate analysis plan will be created for the biomarker analyses.

## 7.9 Safety Analyses

Safety analyses will be performed using the Safety Analysis Set. Safety parameters include AEs, exposure, clinical laboratory parameters (hematology, biochemistry, and urinalysis), vital signs, and ECGs. Summaries of safety parameters will be presented overall as well as by treatment group.

### 7.9.1 Extent of Exposure to Study Medication and Compliance

Descriptive statistics (n, mean, SD, median, minimum, and maximum) will be presented for the number of doses received, the number of days of exposure to study treatment, total dose received, total dose

expected, and dose intensity by treatment group. In addition to summary statistics on the dose intensity as a continuous variable, this will also be categorized into bins: 0-33%, >33-66%, >66-100%, and >100%. Dose intensity and dosing information will be listed.

